Due to the relatively low prevalence, it is possible that 30 subjects meeting inclusion criteria cannot be recruited within the planned 6-month recruitment period or that they are not split roughly equally between the two sites. In that case, we will extend the recruitment period and if required, we will execute the study with as few as 20 subjects, regardless of the distribution between sites. After the study is complete, further research may reveal other potentially interesting biomarkers that should be examined and thus we have included storage of extra blood draws during the study. Given the pilot nature of this study, it is possible that benefits are seen even though results are not conclusive. Study data may be examined more carefully to determine if benefits occur in a distinct subpopulation of subjects (e.g. in PSC patients with UC versus those without).

Overall, considering the known safety data, the implemented risk minimization measures, the expected benefits in the target population, and the unmet medical need for treatment in PSC, the risk-benefit evaluation is considered favorable.

PROTECTION OF HUMAN SUBJECTS

This Human Subjects Research meets the definition of a clinical trial.

I. Risks to Human Subjects

a) Human Subjects Involvement, Characteristics, and Design: A total of 30 adults (age range 18-75 years) who meet the criteria for diagnosis of primary sclerosing cholangitis (PSC), as defined by the American Association for the Study of Liver Diseases (AASLD) published guidelines, will be enrolled into this study from two centers. PSC patients with and without inflammatory bowel disease (IBD) will be included. Other inclusion and exclusion criteria are detailed below:

Inclusion Criteria

- a. Male or female subject age 18-75 years
- b. Diagnosis of PSC consistent with the guidelines published by the AASLD. All subjects must have an elevated serum ALP of at least 1.5 times upper limit of normal (ULN) at baseline plus cholangiographic evidence of PSC (MRI, endoscopic retrograde cholangiography, or direct cholangiography).
- c. Indirect bilirubin <1.2 times the ULN
- d. An ultrasound (or equivalent imaging modality) that excludes biliary obstruction and malignancy within 6 months of study enrollment
- e. PSC with or without inflammatory bowel disease, such as ulcerative colitis or Crohn's disease
- f. Must agree to comply with the study protocol and provide informed consent

Exclusion Criteria

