- a. Pregnancy, attempting to become pregnant, or breastfeeding
- b. Active hepatitis A or B infection
- c. Active hepatitis C infection (antibody positive); patients with a history of hepatitis C infection will be eligible for this study if they have undetectable levels of HCV RNA
- d. HIV/AIDS (per medical record or HIVAb/HIV antigen), tuberculosis, or positive interferon-gamma assay (IGRAs) for *Mycobacterium tuberculosis*
- e. Other cholestatic liver disease such as primary biliary cholangitis and cholestatic diseases of pregnancy
- f. History of metabolic liver diseases such as Wilson's disease, Gilbert's syndrome or hemochromatosis

- g. Serum uric acid levels at Screening >1.2 ULN
- h. Inherited diseases of the liver such as α -1 antitrypsin deficiency
- i. Immunoglobulin G4-related cholangitis
- j. PSC with concomitant autoimmune hepatitis (AIH) and/or primary biliary cholangitis
- k. Secondary sclerosing cholangitis (SSC)
- l. Active acute ascending cholangitis requiring antibiotics
- m. CCA (malignant biliary stricture, neoplasm, and cytology/histopathology or positive fluorescence in situ hybridization (FISH) consistent with adenocarcinoma of the bile duct)
- n. A liver biopsy, if one has been previously obtained, which showed non-alcoholic steatohepatitis (NASH). Patients with suspected fatty liver by imaging will not be excluded.
- o. Presence of complications of advanced PSC such as hepatic encephalopathy, portal hypertension, hepato-renal syndrome, and hepato-pulmonary syndrome
- p. History of liver transplantation, anticipated need for liver transplantation within 12 months from randomization, a Model of End-stage Liver Disease (MELD) score of ≥ 15 , or a Child Pugh score > 6
- q. Ongoing alcohol abuse (> 4 drinks per day for men, and > 2 drinks per day for women)
- r. Moderate-to-severe renal impairment with a calculated creatinine clearance of < 60 mL/min
- s. Any other conditions or abnormalities that, in the opinion of the investigator, may compromise the safety of the subject or interfere with the subject participating in or completing the study
- t. Evidence of, or treatment for, *C. difficile* infection within 30 days before the initiation of the study drug
- u. Evidence of active *C. difficile* infection during the screening phase confirmed by a positive *C. difficile* toxin B
- v. Subjects who have been treated for intestinal pathogens other than *C. difficile* infection within 30 days prior to study drug initiation

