Biliary hyperplasia, or increased cell proliferation in bile ducts, was seen when VC was tested in dog and rat models. In humans, there is no clinical means to test for this effect. When VC was stopped in either animal the bile duct cell proliferation stopped. This side-effect, which was only visible under the microscope, was only seen when the blood levels of VC were significantly higher than what we anticipate in human subjects who enter this clinical trial.

2. Risks related to the disease to be studied (PSC either in the absence or the presence of IBD)

Potential problems that may occur during the clinical trial as part of the natural course of PSC and/or PSC- associated IBD include problems related to PSC biliary strictures. Most PSC patients have strictures in the biliary tree. Dominant strictures can induce stagnation of bile, resulting in bacterial colonization and secondary bacterial cholangitis. This biliary infection, acute ascending cholangitis, is a gastrointestinal emergency with high mortality rates if left untreated. The management is directed at treating the infection with broad-spectrum antibiotics and biliary drainage (endoscopic, percutaneous, or surgical).

Cholangiocarcinoma is a feared complication of PSC. Annual cross-sectional imaging of the liver is currently recommended as standard of care for all PSC patients to screen for cholangiocarcinoma. We recommend liver ultrasound every 6-12 months in all PSC patients. Magnetic resonance imaging of liver (liver MRI) is permissible, but not required.

PSC is often associated with inflammatory bowel diseases, namely ulcerative colitis. Study subjects will undergo clinical assessment for IBD at clinic visits. Study subjects will be instructed to call the study coordinators/investigators to report any new symptoms that may be due to flare up of IBD. Common symptoms that suggest IBD flare up are abdominal pain, fever, bloody stools, and an increase in frequency of bowel movements. In addition, phone monitoring will be performed periodically throughout the study to specifically inquire about the presence of any of these

symptoms. If symptoms are reported, the clinical site investigator may request further diagnostic testing and a clinical evaluation will be required. As symptoms of *Clostridium difficile* colitis may resemble those of an IBD flare-up, *Clostridium difficile* infection needs to be ruled out.

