Overall, the safety profile at the dosage level to be used in this trial is quite positive. An in-depth analysis of the entire clinical database demonstrates that vidofludimus at daily doses below 70 mg is not associated with an increased rate of clinically relevant adverse reactions, including hematuria, relative to placebo. These studies include 233 subjects with rheumatoid arthritis, Crohn's disease, or ulcerative colitis who received daily doses of vidofludimus 20 mg (~3000 treatment days) or vidofludimus 35 mg (~16,500 treatment days) in 3 clinical trials with individual treatment durations of 12-13 weeks.

The investigator will open an IND for the proposed clinical trial. Immunic AG, the drug supplier, will allow the investigator to reference Immunic's IND for vidofludimus calcium (see Letter of Support from Immunic).

2. Protections against risks related to the disease to be studied (PSC either in the absence or the presence of IBD): Acute ascending cholangitis, an acute biliary infection with high mortality rates, is a risk in patients with PSC. Study subjects will be asked about symptoms/signs of ascending cholangitis during clinic visits and phone calls, and subjects will be provided with a list of symptoms and instructed to report the symptoms to the study coordinator immediately if they arise. Symptoms suggestive of acute ascending cholangitis or biliary tree stricture include new onset jaundice, abdominal pain, dark urine, and light-colored stools. Study subjects will be advised to come to the clinic for evaluation or visit the nearest emergency room for consultation with an emergency room physician. If clinical suspicion for acute ascending cholangitis is high, the course of action may include aggressive antibiotic therapy and relief of biliary obstruction (via percutaneous, endoscopic, or surgical intervention), with or without a hospital stay. The Tokyo guidelines are commonly used for the diagnosis of acute ascending cholangitis.

The Tokyo criteria are:

- i. Two of three (fever, right upper quadrant pain, and jaundice), plus
- ii. Systemic inflammation (elevated white blood count and/or C-reactive protein), plus
- iii. Abnormal liver function tests, plus

iv. Imaging detection of biliary dilatation and etiology (stone, stricture, stent, neoplasm)

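### No entry criterion covers recently resolved cholangitis or recent biliary drainage, so an ALP fall from recovery could count in VC's favour; how often is unknown.

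*Combined protocol and SAP*

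**What the plan says.** All references are to the combined protocol and SAP.

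- **Exclusion Criteria, l** bars "Active acute ascending cholangitis requiring antibiotics". It has no look-back period and does not mention drainage.
- **Inclusion Criteria, b** sets the ALP threshold: "All subjects must have an elevated serum ALP of at least 1.5 times upper limit of normal (ULN) at baseline". No repeat value or stability limit is required, and Timeline and Schedule lets screening and baseline fall on the same day.
- **Inclusion Criteria, d** asks for "An ultrasound (or equivalent imaging modality) that excludes biliary obstruction and malignancy within 6 months of study enrollment".
- **Exclusion Criteria, t and v** do use look-backs, for bowel infections: "infection within 30 days before the initiation of the study drug" for *C. difficile* and "infection within 30 days prior to study drug initiation" for other intestinal pathogens.
- **Exclusion Criteria, s** leaves to the investigator any condition that "may compromise the safety of the subject or interfere with the subject participating in or completing the study".
- **Potential Risks, item 2** gives the disease background: "Dominant strictures can induce stagnation of bile, resulting in bacterial colonization and secondary bacterial cholangitis". It names antibiotics and biliary drainage as the management. The Tokyo list, under protections against disease-related risks, includes "Abnormal liver function tests, plus" and imaging evidence of biliary dilatation.
- **Study Design and Methodology** describes a single-arm, open-label study of 30 subjects. Risk Mitigation and Alternative Strategies allows as few as 20.
- **Two response definitions** appear. The protocol body counts a 25% ALP improvement with AST worsening of no more than 33% at 6 months. The Statistical Analysis Plan makes the 6-month ALP normalization rate primary and defines success as a 95% CI that excludes zero, with exact binomial intervals.

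**The concern.** A patient whose antibiotics have ended, or whose stricture was recently drained, is no longer an active case under exclusion l. If ALP is still at least 1.5 x ULN on the day it is measured, that patient can enter while ALP is already falling. The fall would have begun before the first dose. This differs from measurement noise around the entry cut and from a co-treatment started during the study.

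A control arm would show how much ALP falls without VC, and this trial has none. The protocol expects full normalization to be unlikely within 6 months, so few true normalizers are expected. A single patient who normalizes for another reason could then decide the SAP result.

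**Working it through.** The plan gives no null rate, target rate or power, so it has no figure of its own to reproduce. The check has four steps.

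**1. Does any criterion stop a recovering patient?**

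| Provision | Covers | Closes the gap? |
|---|---|---|
| Exclusion l | Active cholangitis needing antibiotics | No, once the episode has resolved |
| Inclusion b | One baseline ALP, at least 1.5 x ULN | No; no stability check |
| Inclusion c | Indirect bilirubin | No; direct bilirubin has no entry limit |
| Inclusion d | Obstruction on imaging up to 6 months old | No; imaging may predate the event, or follow relief of the obstruction |
| Exclusions o, p | Advanced disease | No |
| Exclusion s, and Table 3 history, medication and complication checks | Lets a site notice and decline | Permitted, not required |

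**2. When would a natural fall count?**

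- Entry at exactly 1.5 x ULN: a 25% fall gives 1.5 x 0.75 = 1.125 x ULN, which meets the ALP part of the protocol-body criterion. Reaching 1.0 x ULN needs 1 - 1/1.5 = 33%.
- Assumed case: entry at 2.0 x ULN, settling at 1.2 x ULN. The fall is (2.0 - 1.2)/2.0 = 40%. This meets the ALP part of the protocol-body criterion, but 1.2 x ULN is not normal, so the patient is a non-responder on the SAP primary.

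**3. How many normalizers does SAP success need?** For x = 1 the exact (Clopper-Pearson) lower 95% limit is 1 - 0.975^(1/n).

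| Normalizers/n | Exact 95% CI | Excludes zero? |
|---|---|---|
| 0/30 | 0 to 11.6% | No |
| 1/30 | 0.08% to 17.2% | Yes |
| 0/20 | 0 to 16.8% | No |
| 1/20 | 0.13% to 24.9% | Yes |

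One normalizer is enough at either sample size.

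**4. What might that imply?** Let f be the share of entrants who are recovering and q the chance that such a patient is normal at 6 months without any drug effect. Assume nobody else normalizes. Then P(success with no drug effect) = 1 - (1 - fq)^n. Neither f nor q is in the documents; all values below are assumptions.

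| f | q | n = 30 | n = 20 |
|---|---|---|---|
| 3.3% | 10% | 9% | 6% |
| 5% | 25% | 31% | 22% |
| 10% | 25% | 53% | 40% |
| 15% | 50% | 90% | 79% |

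The effect on mean percent change is smaller. If 1 of 30 falls 25% naturally, the mean moves by 25/30 = 0.8 points. If 3 of 30 fall 50%, it moves by 3 x 50/30 = 5.0 points.

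**The case against.** The strongest reply is that the documents do not supply the key step. They describe ongoing inflammation and list strictures and cholangitis as possible events. They do not call PSC episodic, and the Tokyo item on liver tests does not name ALP, a size of rise or a recovery time. A temporarily raised ALP is plausible, but it is an inference. This stands: it leaves the eligibility gap in place but removes any document-based estimate of its size.

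Second, sites are not blind to recent events. Table 3 schedules medical history at screening, and medication review and assessment for PSC complications at both screening and baseline. Exclusion s lets the investigator decline a patient. ALP is also measured about every 4 weeks, so an early fall in a patient with a known recent episode can be examined. This stands in part: none of it requires the patient to be turned away, exclusion s does not name an unstable ALP, and without controls such a look cannot assign the fall to a cause.

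Third, a patient diagnosed by the Tokyo list would have newer imaging showing dilatation, so relying on an older clear scan is a strained reading of inclusion d. That is fair, but the wording allows it, and imaging after drainage may show no obstruction.

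Fourth, this is a small exploratory pilot, and the larger defect is a success rule that one normalizer satisfies. An assumed 1% background normalization rate alone gives 1 - 0.99^30 = 26% false success at n = 30 and 18% at n = 20. This stands, and it is a reason not to rate the eligibility gap by the weakness of that rule.

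**Conclusion.** The gap is real and worth closing. Nothing in the entry criteria requires a site to defer a patient still recovering from cholangitis or drainage, and the design cannot separate that recovery from a VC effect. Recovery from an event before baseline would favour VC. The size is unknown: the 6% to 90% range above only reflects the assumed f and q and is not evidence of magnitude.

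Four stronger readings are tempting but unsupported:

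- **Each such patient adds 1/30 = 3.3 points to the primary response rate.** This holds only if ALP becomes normal and would not have done so otherwise. A patient settling at 1.2 x ULN adds nothing to the SAP primary.
- **The bias in the trial runs only one way.** That applies to recovery from events before baseline. Potential Risks also describes strictures and cholangitis arising during the trial, and an event near month 6 could work against VC.
- **Thirty days is the right window.** Criteria t and v concern bowel infections, and nothing in the documents ties 30 days to the time ALP needs to settle.
- **Closing the gap makes the SAP success rule sound.** It does not. That rule, and the conflict between the two response definitions, need their own correction.

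**What to change.** Extend exclusion l to any acute cholangitis episode, and any endoscopic, percutaneous or surgical biliary drainage, within a fixed look-back before baseline. The sponsor should choose the length and justify it by how long ALP takes to settle; the 30 days in criteria t and v is only an internal precedent. Also require that the baseline ALP and the inclusion d imaging both postdate any such event.

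The cost is eligibility wording. The history and complication checks in Table 3 should already bring out the information needed. A few patients would wait or be re-screened, which may slow recruitment slightly; the protocol already allows the recruitment period to be extended.
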